**Study Population:**

Describe the characteristics of the subject population, including age range, gender, ethnic background and health status. Identify the criteria for inclusion and exclusion.

Provide the following information:

- A description of the subject selection criteria and rationale for selection in terms of the scientific objectives and proposed study design;
- A compelling rationale for proposed exclusion of any sex/gender or racial/ethnic group;
- Justification for the inclusion of vulnerable groups such as children, prisoners, adults with impaired consent capacity, or others who may be vulnerable to coercion or undue influence.

Please consider these resources:

[NIH Diversity Policy](#)

[FDA Diversity Guidance](#) 

CARE2HOPE covers the following counties: Rowan, Bath, Morgan, Menifee, Elliott, Lee, Owsley, Wolfe, Perry, Letcher, Leslie, Knott. We will recruit participants at all seven jails serving the 12 CARE2HOPE counties; these jails are either located in our CARE2HOPE counties (N=5; Rowan, Lee, Perry, Leslie, Letcher), or our counties have contracts with them to incarcerate their residents (N=2; Montgomery, Clark). To be eligible to take part in Project START-C2H, an individual must:

EITHER:

- (1) be a participant in the CARE2HOPE longitudinal survey (IRB Protocol #43520) who consented to be contacted for future research; and
- (2) be a resident of or anticipate being released to one of the 12 CARE2HOPE counties randomized to intervention or control data collection; and
- (3) be incarcerated in a local jail and expected to be released in <21 days;

OR:

- (1) Be a resident of or anticipate being released to one of the 12 CARE2HOPE counties randomized to intervention or control data collection
- (2) Have used opioids to get high in the 30 days before they were incarcerated, or have injected any drug to get high during that period;
- (3) Be aged 18 or older
- (4) be incarcerated in a local jail and expected to be released in <21 days

We have the opportunity to offer the intervention to individuals enrolled in the comparison counties who have completed 3-month surveys, and feel that offering them this intervention is an ethical best practice. We are not proposing any additional quantitative data collection with them, but these individuals will be eligible for qualitative interviews as part of our continuous quality improvement component.

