**CQI**

We will involve three groups of participants for CQI:

a) Pharmacists. Inclusion criteria: pharmacists from CARE2HOPE counties trained by the program on Vivitrol dispensing (one pharmacist per county, N=12). Exclusion criteria: none

b) Study staff – Rural Health Navigators (REHNs). Inclusion criteria: program staff delivering the intervention to the participants (N=6). Exclusion criteria: none.

c) Current START-C2H participants. Inclusion criteria: 1) being a START-C2H trial participant; and 2) participation in at least two START-C2H health linkage intervention sessions. Exclusion criteria: None.

(Note: REHNs are referred to as Re-Entry Health Navigators for our jail-based activities and Rural Health Navigators for our community-based activities.)

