#### CQI

Pharmacists: Using the contact information from the program records, Graduate Research Assistants, Emory University, will invite the pharmacists trained by CARE2HOPE study on Vivitrol dispensing via e-mails and follow-up phone calls.

REHNs (research study staff): Graduate Research Assistants, Emory University, will invite the REHNs to take part via e-mail and follow-up phone calls. To avoid undue pressure, REHNs' decisions to enroll or refuse to participate will be kept confidential from the study leadership and management team (MPis [name] and [name], Project Director, [name] and Project Manager, [name]).

START-C2H participants: We will stratify the study roster from the REDCap database by county (n=12), then by gender (women and men), then by pharmacy-based Vivitrol participation status (Yes or No), resulting in 48 strata. Next, we will randomly select one participant from each stratum and will contact them using contact information from the study database. We will invite these individuals via phone; if a participant from a particular stratum refuses to participate, we will randomly select a replacement from the same stratum. Prior to the phone calls by the research assistants, our Re-entry Health Navigators (REHNs) will notify all eligible participants (i.e., those who participated in at least two START-C2H health linkage intervention sessions) about the forthcoming CQI interviews. This notification will be sent via text message to participants' phones using contact information from the study database or through Facebook Messenger (private CARE2HOPE account). This short notification will inform the participants that CARE2HOPE research assistants will call them to invite them for the interview and clarify that participation is voluntary. The notification text is provided as an attachment. Each REHN will provide their own phone numbers as part of the text.

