### Qualitative data analysis with START-C2H intervention cohort:

**Qualitative Analysis Plan:** We will use constructivist grounded theory (CGT) methods to develop grounded theories about the perceived relationships and pathways linking (or failing to link) the intervention and changes in primary and secondary outcomes (or lack thereof). CGT provides rigorous methods that will (1) foster *discovery*; (2) elicit *rich descriptions* of participants' experiences of primary and secondary outcomes and of each intervention component; (3) support the creation of *grounded theories* about *perceived pathways* through which these phenomena influence one another; and (4) support comparisons of #1-#3 by participant age gender etc. We will use 3 CGT stages: open coding, axial coding, and theoretical coding.

**Open coding:** The open coding stage is designed to develop a rich understanding of salient phenomena by systematically and comprehensively labelling and defining concepts of interest in the transcripts. In the open coding process, [name] and the GRA will iterate between developing code labels, code definitions, and codebooks independently (to enhance feasibility), and meeting to develop consensus (to enhance validity); they will double code every 3rd transcript. Line-by-line analyses, conducted in NVIVO, will both explore intervention components and primary and secondary outcomes, and also be open to discovering new phenomena that are salient to the aims.

**Axial Coding:** The purpose of Axial Coding is to develop high-level categories that are more abstract than the "open coded" phenomena, and are both internally coherent and distinct from one another. During Axial Coding, categories are defined, and their properties and dimensions identified (i.e., their characteristics and the ways in which they vary, respectively). The GRA and [name] will iterate between independent analyses of open-coded transcripts, and consensus building about emerging learnings. They will independently develop a Category Memo for each emerging category that (1) defines it; (2) identifies and defines its properties and dimensions and possible subcategories; (3) inventories associated codes; and (4) describes how the category differs from other similar categories under development. [name] and the GRA will meet weekly to review one another's emerging findings and memos, and develop a suite of consensus categories,

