We will use the constant comparison method to systematically compare findings across participant subgroups (e.g., defined by gender, houselessness status). To support these comparisons, we will color-code each relational chart by these subgroup characteristics. When we find variation across subgroups, we will return to the data to identify conditions and contingencies that may explain these variations, and expand relational statements accordingly, or the categories they link. As needed, we will present different sets of relational statements for specific subgroups. These relational statements will form the foundations of grounded theories exploring perceptions of each intervention component's effect on each outcome, and the pathways through which it does (or does not) operate to change primary and secondary outcomes, for particular subgroups.

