Triangulating across qualitative and quantitative findings: We will use joint displays to systematically compare and contrast qualitative and quantitative findings for each intervention component/outcome relationship (e.g., preliminary [i.e.,  $p < 0.10$ ] hypothesis test results about the relationship of receiving FTS to subsequent overdose vs. qualitative grounded theory about this same relationship). When qualitative and quantitative findings both suggest an ameliorative relationship, we will conclude that the available evidence supports a beneficial effect. When both find an adverse relationship, we will conclude that the evidence indicates a harmful effect. When neither suggests a relationship, we will conclude that the evidence indicates no effect. When quantitative and qualitative results diverge, we will return to the qualitative and quantitative data to learn if we can resolve this discrepancy. Qualitative data may illuminate an unexpected confounder for the quantitative hypothesis test. Alternatively, qualitative data may suggest that the intervention only has an effect in one subgroup (e.g., individuals residing in counties with more services) and the quantitative findings reach a null conclusion because the quantitative sample is small, and includes both people who do and do not live in such counties. We will seek to systematically explore all divergences using these tables, and seek to refine relational statements and grounded theories accordingly. We will rely solely on qualitative data to learn whether the intervention effect is attenuated in a subgroup (e.g., women), given that the quantitative sample is underpowered to detect effect moderation.

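### Whether the effect is weaker in a subgroup is to be learned solely from interviews with treated, engaged participants, which can show perceived differences but not effect modification

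*Combined protocol and SAP*

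**What the plan says.** The SAP's closing paragraph, on triangulating qualitative and quantitative findings, gives the rule: "We will rely solely on qualitative data to learn whether the intervention effect is attenuated in a subgroup", with women as the example. The reason follows: "given that the quantitative sample is underpowered to detect effect moderation". The quantitative model in the SAP's exploratory analysis section contains Time, Int and Time × Int, and no subgroup term.

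Four places define the interview data:

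- The SAP section is titled "Qualitative data analysis with START-C2H intervention cohort".
- The protocol's Study Population section (CQI, group c) requires "participation in at least two START-C2H health linkage intervention sessions".
- Subject Recruitment Methods & Advertising (CQI) stratifies by county, gender and pharmacy Vivitrol status, "resulting in 48 strata. Next, we will randomly select one participant from each stratum".
- Study Population adds comparison-county participants who are offered the intervention after their 3-month survey: "these individuals will be eligible for qualitative interviews as part of our continuous quality improvement component". The two-session criterion applies to them as well.

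Subgroups are compared within these interviews: "We will use the constant comparison method to systematically compare findings across participant subgroups".

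**The concern.** An attenuated effect is a difference between subgroups in the intervention-versus-comparison contrast. Interviews with people who have all received the intervention contain no such contrast. If women describe less benefit than men, that may reflect a smaller effect. It may equally reflect a different course that would have occurred without the intervention, different expectations, or different willingness to credit the programme. The interviews cannot separate these.

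The two-session rule adds a selection. People who attended none or one of the four sessions are outside the sample, and the effect might be weaker in them. If disengagement differs by subgroup, the interviews would not reveal it.

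The conclusion has consequences within the plan. The same SAP paragraph allows interviews to explain a null quantitative result by suggesting that the intervention works only in one subgroup, for example in counties with more services. With no subgroup estimate planned, nothing quantitative checks that explanation.

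**Working it through.** **Inputs.** From the SAP power paragraph: 12 counties, 20 participants each (240 in all), ICC 0.05, within-person autocorrelation 0.35, alpha 0.10, and power 0.80 at a standardized difference of 0.55. From Study Design (COVID-19 Policies): six counties against six. Assumed here: two-sided alpha (the SAP does not say), each county counted in one arm, no attrition, and an even subgroup split within county. Gender roughly fits the last, since Study Population expects slightly more than half to be men.

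**Step 1: reproduce the SAP's figure.** The SAP does not give its variance formula. The following uses all its inputs and matches.

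- Change-score variance: 2 × (1 − 0.35) = 1.30
- Design effect: 1 + (20 − 1) × 0.05 = 1.95
- Per arm: 6 × 20 = 120
- SE of the Time × Int effect: √(2 × 1.30 × 1.95 / 120) = 0.2055
- Power at 0.55 from a noncentral t with 12 − 2 = 10 df: 0.801

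The SAP's 0.80 is reproduced.

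**Step 2: SE of a subgroup interaction.** An even split gives four cells (arm × subgroup) of 60.

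- County effect cancels within county: √(4 × 1.30 / 60) = 0.294
- Full design effect kept: √(4 × 1.30 × 1.95 / 60) = 0.411

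**Step 3: power and precision** (normal quantiles, 1.645 and 0.842). A half attenuation means 0.55 SD in one subgroup and 0.275 SD in the other, an interaction of 0.275.

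| | County effect cancels | Design effect 1.95 kept |
|---|---|---|
| Power, half attenuation: Φ(0.275/SE − 1.645) | 0.239 | 0.165 |
| Power, interaction of 0.55: Φ(0.55/SE − 1.645) | 0.588 | 0.379 |
| Interaction needed for 80% power: 2.487 × SE | 0.73 SD | 1.02 SD |
| 90% half-width: 1.645 × SE | 0.48 SD | 0.68 SD |

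A subgroup holding a share p of the sample widens the interval by 1/(2√(p(1 − p))). At p = 0.25 this is 1.15, giving about 0.56 to 0.78 SD.

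**Step 4: what the interviews hold.** 12 counties × 2 genders × 2 Vivitrol strata = 48 strata. One person from each gives at most 24 women and 24 men, fewer if a stratum is empty. None is untreated at interview.

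**The case against.** The strongest defence is that the premise is right. With power of about 0.17 to 0.24 for a half attenuation, leaving out interaction tests in a small trial already labelled exploratory is a defensible choice. The SAP also generally frames its qualitative aim as perceived effectiveness and perceived pathways, and the protocol's Research Procedures section treats the interviews as a complement to the quantitative evidence. The verb in the disputed sentence is learn, not decide. All of this stands. It narrows the fault to one sentence that drops the limit to perceptions and excludes quantitative evidence. Low power argues against leaning on a significance test; it does not make a source without a comparison able to answer the question.

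A reader might infer more than the documents support:

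- *That selecting engaged participants tilts the plan toward declaring benefit.* A benefit conclusion requires both sources to point that way. Favourable interviews with a null quantitative result count as divergence and trigger re-examination. Selection alone can at most block a no-effect conclusion. The coding plan also looks for pathways that fail.
- *That the intervention failed in people with fewer than two sessions.* Nothing in the documents shows this. The effect might be weaker in them, and the interviews cannot tell.
- *That the interval would be about ±0.73 SD.* Back-calculating with normal quantiles gives 0.55 / 2.487 = 0.221, doubled to 0.442, times 1.645 = 0.73. But the SAP's power figure reproduces with t on 10 df and an SE of 0.2055, and for a within-county characteristic much of the county effect may cancel. The supported range is 0.48 to 0.68.
- *That interviews should be reallocated to low attenders.* This would change an inclusion criterion and the stratified draw. Collection was planned for five months from a target start of February 2022, so it may come too late.

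**Conclusion.** The point holds as a limited one. As written, the sentence gives the question of effect modification to data that cannot answer it: at most 48 treated participants, each with at least two sessions and no concurrent comparison group. Former comparison participants who later received the intervention may be among them, but they do not supply that comparison.

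The SAP's statement that a moderation test is underpowered is confirmed. An estimate remains available from data already being collected, with an interaction SE of about 0.29 to 0.41 SD. Such an interval is wide and would rarely settle the question, but it shows how little is known, which a qualitative-only answer does not. The figures rest on the assumptions listed in the working; attrition or an uneven split would widen them. The estimate would also depend on the missing-data assumptions behind the planned multiple imputation. The main analysis is unaffected, and the severity is minor.

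**What to change.** 1. In the SAP's exploratory quantitative analysis section, name a short prespecified list of subgroups (gender, for example). Report each Time × Int × subgroup estimate with its 90% interval, labelled exploratory. Make no claim from significance or its absence, and state that the estimates are subject to the missing-data assumptions.
2. Reword the sentence in the triangulation paragraph so that the qualitative data describe perceived subgroup differences and generate hypotheses about why effects may differ, not whether the effect is attenuated. State as a limitation that interviewees had all attended at least two sessions.

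The cost is a few more model runs, some SAP wording, and wide intervals that must be presented as exploratory. No new data and no change to interview sampling are needed.
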